Appendix 2 National Early Warning Score (NEWS)

The NEWS has demonstrated an ability to discriminate patients at risk of poor outcomes. This score is based on 7 clinical parameters (respiration rate, oxygen saturation, any supplemental oxygen, temperature, systolic blood pressure, heart rate, level of consciousness [Alert, Voice, Pain, Unresponsive]). To calculate you may access <https://www.mdcalc.com/national-early-warning-score-news>

Details are also provided below.

Formula: Addition of the selected points; points assigned below:

Criteria	Point Value
Respiratory Rate (breaths per minute)	
≤8	+3
9-11	+1
12-20	0
21-24	+2
≥25	+3
Oxygen Saturation (%)	
≤91	+3
92-93	+2
94-95	+1
≥96	0
Any Supplemental Oxygen	
Yes	+2
No	0
Temperature in °C (°F)	
≤35.0 (95)	+3
35.1-36.0 (95.1-96.8)	+1
36.1-38.0 (96.9-100.4)	0
38.1-39.0 (100.5-102.2)	+1
≥39.1 (≥102.3)	+2

GRIFOLS		Number	BIG-CL-PRT-000020	Version	4.0	Status	Effective	Effective Date	19-Jul-2021	Page	82 of 91												
GC2007 - A Multicenter, Randomized, Open-label Parallel Group Pilot Study to Evaluate Safety and Efficacy of High Dose Intravenous Immune Globulin (IVIG) plus Standard Medical Treatment (SMT) versus SMT alone in																							
Systolic BP																							

 
 ≤90	+3	
 
 91-100	+2	
 
 101-110	+1	
 
 111-219	0	
 
 ≥220	+3	
 
												≤90	+3	91-100	+2	101-110	+1	111-219	0	≥220	+3		
≤90	+3																						
91-100	+2																						
101-110	+1																						
111-219	0																						
≥220	+3																						
Heart Rate (beats per minute)																							

 
 ≤40	+3	
 
 41-50	+1	
 
 51-90	0	
 
 91-110	+1	
 
 111-130	+2	
 
 ≥131	+3	
 
												≤40	+3	41-50	+1	51-90	0	91-110	+1	111-130	+2	≥131	+3
≤40	+3																						
41-50	+1																						
51-90	0																						
91-110	+1																						
111-130	+2																						
≥131	+3																						
AVPU																							

 
 A	0	
 
 V, P, or U	+3	
 
												A	0	V, P, or U	+3								
A	0																						
V, P, or U	+3																						

AVPU, Alert, Voice, Pain, Unresponsive.

Interpretation:

1. A low score (NEWS 1–4) should prompt assessment by a competent registered nurse who should decide if a change to frequency of clinical monitoring or an escalation of clinical care is required.
2. A medium score (i.e. NEWS of 5–6 or a RED score) should prompt an urgent review by a clinician skilled with competencies in the assessment of acute illness – usually a ward-based doctor or acute team nurse, who should consider whether escalation of care to a team with critical-care skills is required (i.e. critical care outreach team). °A RED score refers to an extreme variation in a single physiological parameter (i.e., a score of 3 on the NEWS chart in any one physiological parameter, colored RED to aid identification; e.g., heart rate
3. A high score (NEWS ≥ 7) should prompt emergency assessment by a clinical team/critical care outreach team with critical-care competencies and usually transfer of the patient to a higher dependency care area.

GRIFOLS	Number	BiG-CL-PRT-000020	Version	4.0	Status	Effective	Effective Date	19-Jul-2021
	GC2007 - A Multicenter, Randomized, Open-label Parallel Group Pilot Study to Evaluate Safety and Efficacy of High Dose Intravenous Immune Globulin (IVIG) plus Standard Medical Treatment (SMT) alone in							
	Bioscience Industrial Group						Page	83 of 91

Evidence Appraisal

The six physiological parameters that were proposed to form the basis standardized National Early Warning Score were derived from this study. It retrospectively analyzed data from 35,585 medical admissions.

Original/Primary Reference

Research Paper Royal College of Physicians. National Early Warning Score (NEWS) Standardising the assessment of acute-illness severity in the NHS. Report of a working party. London: RCP, 2012.

Validation

Other References

Appendix 3 Acute Respiratory Distress Syndrome (ARDS) Berlin Definition

The Berlin Definition of Acute Respiratory Distress Syndrome is summarized in the table below. Timing is usually within 1 week of a known clinical insult or new or worsening respiratory symptoms.

Number	Version	Status	Effective Date	Page
GRIFOLS	4.0	Effective	19-Jul-2021	84 of 91
GC2007 - A Multicenter, Randomized, Open-label Parallel Group Pilot Study to Evaluate Safety and Efficacy of High Dose Intravenous Immune Globulin (IVIG) plus Standard Medical Treatment (SMT) versus SMT alone in				
Chest imaging ^a				Bilateral opacities—not fully explained by effusions, lobar/lung collapse, or nodules
Origin of edema				Respiratory failure not fully explained by cardiac failure or fluid overload Need objective assessment (eg, echocardiography) to exclude hydrostatic edema if no risk factor present
Oxygenation ^b ,				Mild $200 \text{ mm Hg} < \text{PaO}_2/\text{FIO}_2 \leq 300 \text{ mm Hg}$ with PEEP or CPAP $\geq 5 \text{ cm H}_2\text{O}$ Moderate $100 \text{ mm Hg} < \text{PaO}_2/\text{FIO}_2 \leq 200 \text{ mm Hg}$ with PEEP $\geq 5 \text{ cm H}_2\text{O}$ Severe $\text{PaO}_2/\text{FIO}_2 \leq 100 \text{ mm Hg}$ with PEEP $\geq 5 \text{ cm H}_2\text{O}$

Abbreviations: CPAP, continuous positive airway pressure; FIO₂, fraction of inspired oxygen; PaO₂, partial pressure of arterial oxygen; PEEP, positive end-expiratory pressure.

a. Chest radiograph or computed tomography scan.

b If altitude is higher than 1000 m, the correction factor should be calculated as follows: [PaO₂/FIO₂ X (barometric pressure/760)].

c This may be delivered noninvasively in the mild acute respiratory distress syndrome group.

The following may be used for the Berlin criteria, **for patients who are Not on a ventilator and do not have a blood gas performed. Since the effect of positive end-expiratory pressure (PEEP) may modify the derivation of SaO_2 to SpO_2 , please do Not use SpO_2 to apply Berlin criteria to patients while on a mechanical ventilator.**

Respiratory Thresholds Determined by Pulse Oximetry Measurement of O₂ Saturation (for patients Not on mechanical ventilation)

PaO ₂ /FiO ₂	Corresponding SpO ₂ /FiO ₂ Threshold
≥ 400	≥ 91.2
<400	<91.2
<300	<85.7

GRIFOLS	Number	BiG-CL-PRT-000020	Version	4.0	Status	Effective	19-Jul-2021
	GC2007 - A Multicenter, Randomized, Open-label Parallel Group Pilot Study to Evaluate Safety and Efficacy of High Dose Intravenous Immune Globulin (IVIG) plus Standard Medical Treatment (SMT) versus SMT alone in Bioscience Industrial Group					Page	85 of 91

PaO₂/FiO₂	Corresponding SpO₂/FiO₂ Threshold
<200	<214
<100	<89

Derivation of SpO₂/FiO₂ values corresponding to PaO₂/FiO₂ ratios in the combined anesthesia and ARMA database* [*Data derived from 4728 matched SpO₂/FiO₂ and PaO₂/FiO₂ measurements from the combined anesthesia and ARMA database]

References

ARDS Definition Task Force. Acute Respiratory Distress Syndrome - The Berlin Definition. JAMA. 2012;307(23):2526-2533. doi:10.1001/jama.2012.5669

Appendix 4 Sequential Organ Failure Assessment (SOFA) Score

SOFA Score

Variable	0	1	2	3	4
Score (0-4)					
PaO ₂ /FiO ₂ mmHg	≥ 400	< 400	< 300	< 200	< 100
Platelets, x 10 ³ /µL (x 10 ⁶ /L)	≥ 150 (> 150)	< 150 (< 150)	< 100 (< 100)	< 50 (< 50)	< 20 (< 20)
Bilirubin, mg/dL (µmol/L)	< 1.2 (< 20)	1.2 - 1.9 (20 - 32)	2.0 - 5.9 (33 - 100)	6.0 - 11.9 (101 - 203)	≥ 12 (> 203)
Hypotension	None	MABP < 70 mmHg	Dop < 5	Dop 6 - 15 or Epi < 0.1 or Norepi < 0.1	Dop > 15 or Epi > 0.1 or Norepi > 0.1
Glasgow Coma Scale Score	15	13 - 14	10 - 12	6 - 9	< 6
Creatinine, mg/dL (µmol/L)	< 1.2 (< 106)	1.2 - 1.9 (106 - 168)	2.0 - 3.4 (169 - 300)	3.5 - 4.9 (301 - 433)	≥ 5 (> 434)
TOTAL (0 - 24):					

Dopamine [Dop], epinephrine [Epi], and norepinephrine [Norepi] doses in µg/kg/min (administered for at least one hour). MABP, mean arterial blood pressure; SI units in parentheses ()

The following may be used to calculate the Respiratory item of the SOFA score, **for patients who are Not on a ventilator and do not have a blood gas performed. Since the effect of positive end-expiratory pressure (PEEP) may modify the derivation of SaO₂ to SpO₂, please do Not use SpO₂ in the SOFA calculation for patients while on a mechanical ventilator.**

SOFA Respiratory Score Determined by Pulse Oximetry Measurement of O₂ Saturation (for patients Not on mechanical ventilation)

SOFA Respiratory Item score	PaO ₂ /FiO ₂	SpO ₂ /FiO ₂ Threshold for scoring
0	≥ 400	≥ 512
1	<400	<512
2	<300	<357

GRIFOLS Bioscience Industrial Group	Number	BLG-CL-PRT-000020	Version	4.0	Status	Effective	19-Jul-2021	Page	87 of 91									
	GC2007 - A Multicenter, Randomized, Open-label Parallel Group Pilot Study to Evaluate Safety and Efficacy of High Dose Intravenous Immune Globulin (IVIG) plus Standard Medical Treatment (SMT) versus SMT alone in																	
Derivation of SpO ₂ /FiO ₂ values corresponding to PaO ₂ /FiO ₂ ratios in the combined anesthesia and ARMA database* [*Data derived from 4728 matched SpO ₂ /FiO ₂ and PaO ₂ /FiO ₂ measurements from the combined anesthesia and ARMA database]																		
Glasgow Coma Scale																		
				Criteria	Score													
				Best Eye Response (1 – 4)														
				No eye opening	1													
				Eye opens to painful stimulus	2													
				Eye opens to verbal command	3													
				Eyes open spontaneously	4													
				Best Verbal Response (1 – 5)														
				No verbal response	1													

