10. Known history of prothrombin gene mutation 20210, homozygous Factor V Leiden mutations, antithrombin III deficiency, protein C deficiency, protein S deficiency or antiphospholipid syndrome.
11. Presence of malignancy (either new diagnosis of malignancy or known residual disease) within the past 12 months (note: exceptions for non-melanoma skin cancer and carcinoma in situ of cervix are allowed)
12. Creatinine at Screening is \geq 4 mg/dL (or subject is dependent on dialysis/renal replacement therapy)
13. Known Immunoglobulin A (IgA) deficiency with anti-IgA serum antibodies
14. Uncontrolled hypertension at the time of Screening (systolic blood pressure $>$ 200 mm Hg) or refractory severe hypotension with sustained systolic blood pressure $<$ 90 mm Hg unresponsive to vasopressors.

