5.3.2 Removal of Subjects

Subjects may withdraw or be withdrawn from the study for the following reasons:

1. At their own request or at the request of their legally acceptable representative.
2. If, in the investigator's opinion, continuation in the study would be detrimental to the subject's well-being.
3. At the specific request of the sponsor.

GRIFOLS Bioscience Industrial Group	Number	BLG-CL-PRT-000020	Version	4.0	Status	Effective	Effective Date	19-Jul-2021	Page	43 of 91
	GC2007 - A Multicenter, Randomized, Open-label Parallel Group Pilot Study to Evaluate Safety and Efficacy of High Dose Intravenous Immune Globulin (IVIG) plus Standard Medical Treatment (SMT) versus SMT alone in									

Also, subjects may be withdrawn for the following reasons:

1. The subject is not able to adhere to the main protocol requirements (major protocol violations).
2. The occurrence of an AE which in the investigator's opinion requires the withdrawal of the subject from the clinical trial.
3. The subject is lost to follow-up.
4. Subject's death.
5. Any event which in the opinion of the investigator impedes the subject's participation in the study.

With regard to individual subject criteria for discontinuation of Gamunex-C IV infusions, discontinuation of study drug treatment will occur if the subject develops any of the following:

- Evidence of hypersensitivity/anaphylaxis to Gamunex-C
- Occurrence of thromboembolic complication (e.g., pulmonary embolism) whether or not related to COVID-19
- Hypertensive emergency with sustained systolic blood pressure > 200 mm Hg unresponsive to intervention or refractory severe hypotension with sustained systolic blood pressure < 90 mm Hg unresponsive to vasopressors
- Development of renal failure with creatinine ≥ 4 mg/dL (or subject becomes dependent on dialysis/renal replacement therapy)

In all cases, the reason for withdrawal must be recorded in the study record and in the subject's records.

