8.3.1 Warnings/Precautions

True hypersensitivity reactions from IVIG administration are rare. They can occur in subjects with anti-IgA antibodies. Rarely, human normal immunoglobulin can induce a fall in blood pressure with anaphylactic reaction, even in subjects who had tolerated previous treatment with human normal immunoglobulin.

There is clinical evidence of an association between IVIG administration and thromboembolic events such as myocardial infarction, cerebral vascular accident (including stroke), PE, and DVT that is assumed to be related to a relative increase in blood viscosity through the high influx of immunoglobulin in at-risk subjects. In subjects at risk for thromboembolic adverse reactions, IVIG products should be administered at the minimum rate of infusion and dose practicable.

Cases of acute renal failure have been reported in subjects receiving IVIG therapy. In most cases, risk factors have been identified, such as pre-existing renal insufficiency, diabetes mellitus, hypovolemia, overweight, concomitant nephrotoxic medicinal products, or age over 65. In case of renal impairment, IVIG discontinuation should be considered. While these reports of renal dysfunction and acute renal failure have been associated with the use of many of the licensed IVIG products containing various excipients such as sucrose, glucose, and maltose, those containing sucrose as a stabilizer accounted for a disproportionate share of the total number. In subjects at risk, the use of IVIG products that do not contain these excipients may be considered. Gamunex-C *does not* contain sucrose, maltose, or glucose.

AMS has been reported to occur in association with IVIG treatment. The syndrome usually begins within several hours to 2 days following IVIG treatment.

Gamunex-C may contain blood group antibodies which may act as hemolysins and induce in vivo coating of red blood cells with immunoglobulin, causing a positive DAT and, rarely, hemolysis. Hemolytic anemia can develop subsequent to IVIG therapy due to enhanced red blood cells sequestration. IVIG recipients should be monitored for clinical signs and symptoms of hemolysis. If these are present after IVIG infusion, perform appropriate confirmatory laboratory testing.

In subjects receiving IVIG, there have been some reports of acute non-cardiogenic pulmonary oedema (Transfusion Related Acute Lung Injury [TRALI]). TRALI is characterized by severe hypoxia, dyspnoea, tachypnoea, cyanosis, fever and hypotension.

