Combination arm: Gamunex-C 2 g/kg (total) may be given either as 500 mg/kg in divided doses over 4 consecutive days OR 400 mg/kg in divided doses over 5 consecutive days		X ^g	X ^g	X ^g	X ^g	X ^g												

Study Period	Screen/ Baseline	1 st IP	SMT and Daily Evaluations										Follow- Up	Follow-Up Clinic Visit Day			Phone Checks	
			2	3	4	5±1 day	6	7	8	9	10	11-14 Daily if in hospital		15±1 e day	16-28 Daily if in hospital	29 ^{e,f} ± 1 day	Day 60 ± 2 days	Day 90 ± 2 days
Study Day	1																	
Procedures/assessments																		
Record hospital admission and discharge dates	X															X ^h		
Record ICU admission & discharge dates	X															X ^h		
Sequential Organ Failure Assessment (SOFA) score (Appendix 4)	X					X								X		X		
Assessment of ARDS (Berlin Criteria) (Appendix 3)	X					X								X		X		
Daily 24-hour fluid balance (intake and output) while in hospital	X	X	X	X	X	X	X	X	X	X	X							
Respiratory sample for quantitative measurement of SARS-CoV-2 viral load by NAT or PCR (real-time RT-PCR) (obtained via nasopharyngeal swab)	Pre randomized treatment ⁱ					X ⁱ								X		X		
Sample for quantitative measurement of IgM and IgG antibodies to SARS-CoV-2 (store serum samples frozen at -70°C for later analysis at an external lab)	Pre randomized treatment ⁱ					X ⁱ								X		X		
Serum Chemistry (creatinine, albumin, alanine aminotransferase [ALT], total bilirubin, lactate dehydrogenase [LDH])	Pre randomized treatment ⁱ					X ⁱ								X		X		

Number	BIG-CL-PRT-000020	Version	4.0	Status	Effective	Effective Date	19-Jul-2021
GC2007 - A Multicenter, Randomized, Open-label Parallel Group Pilot Study to Evaluate Safety and Efficacy of High Dose Intravenous Immune Globulin (IVIG) plus Standard Medical							
Bioscience Industrial Group							

Study Period	Screen/ Baseline	1 st IP	SMT and Daily Evaluations									Follow- Up	Follow-Up Clinic Visit Day			Phone Checks	
			2	3	4	5±1 day	6	7	8	9	10		11-14 Daily if in hospital	15±1 e day	16-28 Daily if in hospital	29 ^{e,f} ± 1 day	Day 60 ± 2 days
Study Day	1		2	3	4	5±1 day	6	7	8	9	10	11-14 Daily if in hospital	15±1 e day	16-28 Daily if in hospital	29 ^{e,f} ± 1 day	Day 60 ± 2 days	Day 90 ± 2 days
Procedures/assessments																	
Ferritin, CRP, D-dimer	Pre randomized treatment ⁱ						X ⁱ						X		X		

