#### 4.6 Data Derivations and Transformations

The following derivations will be used in this study:

Study Day:

- Date of assessment – date of randomization + 1 for assessments done on or after date of randomization
- Date of assessment – date of randomization for assessments done before date of randomization

Baseline Observation: the last non-missing value prior to randomization.

Duration:

- Duration in days = end date – start date + 1
- Duration in minutes = end time in minutes – start time in minutes

Origin or Start Date for Time to Event Endpoints:

- Time to death: date of randomization
- Time to ICU Discharge (actual and medical equivalence, if applicable): date of randomization or date of ICU admission, whichever was later
- Time to Hospital Discharge (actual and medical equivalence, if applicable): date of randomization
- Time to Clinical Response: date of randomization

Event Date for Time to Clinical Response:

- If a subject met the criteria for clinical response at multiple assessments, the date of the first assessment meeting the definition of clinical response will be used as the event date for deriving time to clinical response.

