### **Assessment of SOFA score**

The SOFA score will be assessed on Days 1, 5, 15, and 29. Change from baseline in SOFA score to Days 5, 15, and 29 will be summarized for each treatment group by visit.

Mean change in SOFA scores through Day 29 will be evaluated by fitting a linear mixed-effects model for repeated measures (MMRM). The model will include change from baseline in SOFA score as the repeated dependent variable; treatment (as a class variable), visit (as a class variable including Days 5, 15, and 29), and treatment-by-visit interaction as fixed effects; baseline SOFA

score, age and gender as covariates; and measures within subject at each visit as a repeated measure. An unstructured covariance matrix will be used to model the within-subject error. If the fit of the unstructured covariance structure fails to converge, a compound symmetry covariance structure will be used. Parameters will be estimated using restricted maximum likelihood with the Kenward-Roger method for calculating the denominator degrees of freedom. Missing data will not be imputed. From this model, the least-squares (LS) means and 95% CIs for each treatment group, the treatment difference in the LS means, the 95% CI for the difference, and the associated p-value will be reported on Days 5, 15 and 29, as well as for the average across all post-baseline visits.

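### The SOFA renal item is scored on creatinine alone with no rule for dialysis, so renal failure that begins after randomisation is under-scored

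*Protocol*

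**What the plan says.** Protocol Appendix 4 gives the renal item as one row, "Creatinine, mg/dL". Below 1.2 scores 0, 1.2 to 1.9 scores 1, 2.0 to 3.4 scores 2, 3.5 to 4.9 scores 3, and 5 or more scores 4. The row has all five cells and no dialysis criterion.

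In SAP section 6.2 (Assessment of SOFA score), "Change from baseline in SOFA score to Days 5, 15, and 29 will be summarized for each treatment group by visit". A mixed model for repeated measures then yields treatment differences with p-values, and "Missing data will not be imputed". Baseline under SAP section 4.6 is "the last non-missing value prior to randomization". SAP section 6.2 has no dialysis rule either.

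The protocol does foresee dialysis. Section 5.2, criterion 12, excludes a screening creatinine of 4 mg/dL or more, or cases where the "subject is dependent on dialysis/renal replacement therapy". Section 5.3.2 stops infusions at the same creatinine, or if the "subject becomes dependent on dialysis/renal replacement therapy". Section 8.3.1 warns: "Cases of acute renal failure have been reported in subjects receiving IVIG therapy".

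**The concern.** Dialysis lowers serum creatinine without any recovery of the kidneys. That premise is general knowledge and is not stated in the documents. A score that reads creatinine alone therefore falls when organ support starts.

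The gap is internal to the protocol. Sections 5.2 and 5.3.2 both treat dialysis dependence as an alternative to a creatinine of 4 mg/dL or more, but Appendix 4 drops that pairing. A subject dialysed to 1.0 mg/dL meets the protocol's own renal criterion for stopping infusions and still scores 0. Appendix 4 does allow for organ support elsewhere: the circulatory item is scored on vasopressor dose, and pulse oximetry is barred for ventilated subjects because positive end-expiratory pressure may distort it.

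At stake is a secondary efficacy comparison with its own p-value. If dialysis use differs between arms, the arm with more renal failure gets a SOFA result that is too favourable.

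**Working it through.** **Inputs.** Cut-offs and the total range of 0 to 24 come from Appendix 4, the baseline rule from SAP section 4.6, the entry limit from protocol section 5.2, and about 100 subjects allocated 1:1 from protocol section 4.2. Dialysis rates and creatinine on dialysis are not given, so they are assumed over a range.

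**The plan's own figure.** Six items × 4 points = 24, which reproduces the stated maximum. The creatinine row is therefore the whole renal item.

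**Highest eligible baseline.** Screening creatinine must be below 4 mg/dL, and screening and baseline are the same Day 1 visit. The baseline renal item is therefore at most 3.

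**Recorded change for one dialysed subject** = item(creatinine at visit) − item(baseline creatinine):

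| Baseline creatinine (item) | Dialysed to 0.9 (0) | 1.5 (1) | 2.5 (2) | 3.7 (3) |
|---|---|---|---|---|
| 0.9 (0) | 0 | +1 | +2 | +3 |
| 1.5 (1) | −1 | 0 | +1 | +2 |
| 2.5 (2) | −2 | −1 | 0 | +1 |
| 3.7 (3) | −3 | −2 | −1 | 0 |

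Improvement is impossible from baseline item 0. From items 1 to 3 it needs a dialysed value in a lower band than baseline. Example: baseline 2.5 (item 2), dialysed to 1.0 (item 0), change 0 − 2 = −2.

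**Understatement** = 4 − item(dialysed creatinine), taking the top score of 4 as the reference. Across the four columns this is 4, 3, 2 and 1 points. At 5 mg/dL or more it is 0.

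**Distortion of the between-arm mean change** = excess proportion on dialysis × points understated. This takes the average understatement per dialysed subject as equal in the two arms. The baseline score cancels, because it is subtracted under either scoring. The figures are for raw means at one visit and only approximate the adjusted model.

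| Assumed excess | 1 point | 2 points | 3 points | 4 points |
|---|---|---|---|---|
| 2% | 0.02 | 0.04 | 0.06 | 0.08 |
| 5% | 0.05 | 0.10 | 0.15 | 0.20 |
| 10% | 0.10 | 0.20 | 0.30 | 0.40 |
| 15% | 0.15 | 0.30 | 0.45 | 0.60 |

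All entries favour the arm with more dialysis.

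**Sign of the recorded difference.** With assumed rates of 10% and 5%, an average recorded renal change of −2 contributes (0.10 − 0.05) × (−2) = −0.10, an apparent benefit. A change of +2 contributes +0.10, which still reads as harm, though too small.

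**Against precision.** If the SD of SOFA change is 3 to 4 (an assumption) with 50 assessed per arm, SE = SD × √(1/50 + 1/50) = 0.2 × SD = 0.6 to 0.8. The distortion then runs from 0.02/0.8 = 0.025 to 0.60/0.6 = 1.0 standard errors.

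**The case against.** A reader might infer that a subject who starts dialysis is always scored as improving, for instance by 3 points when creatinine goes from 4.2 to 1.0 mg/dL. The documents do not support this. Change runs from the last value before randomisation, and 4.2 is above the entry limit, so it can only be a later peak. SOFA is taken only on Days 1, 5, 15 and 29, so that peak may never be scored. In many cases the result is masked worsening.

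A reader might also infer that the product's renal toxicity will appear as SOFA benefit. Protocol section 8.3.1 describes renal failure with IVIG products in general, says that sucrose-containing products accounted for a disproportionate share, and states that Gamunex-C contains no sucrose, maltose or glucose. No dialysis rate or difference between arms is given, so the bias could favour either arm.

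The renal harm is not lost. Renal failure is not among the anticipated COVID-19 symptoms exempt from adverse event recording. SAP sections 7.2.5 and 7.3 tabulate adverse events and creatinine changes, and the safety committee reviews events. SOFA is also one of many secondary endpoints in a pilot without multiplicity control. All this stands and limits the importance of the point, but none of it corrects the SOFA estimate or its p-value.

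Finally, the reference score of 4 is a choice. The protocol pairs dialysis with creatinine of 4 mg/dL or more, which is item 3 or 4. Against a reference of 3, each understatement is one point smaller, and the largest distortion is 0.15 × 3 = 0.45.

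**Conclusion.** The concern holds in a limited form. The creatinine-only rule under-scores renal failure that begins after randomisation by 1 to 4 points while the subject is on dialysis with creatinine below 5 mg/dL. It can read as improvement only if baseline creatinine was 1.2 mg/dL or more and the dialysed value falls in a lower band. Otherwise worsening is masked.

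The comparison is biased towards whichever arm has more dialysis, by 0.02 to 0.60 points over the assumed excesses of 2 to 15 percentage points. This rests on three assumptions: dialysis lowers creatinine, the top renal score is the right reference, and understatement per dialysed subject is similar in the two arms. The size is modest and the direction unknown. The primary mortality analysis is not affected.

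**What to change.** Add the following to protocol Appendix 4 and SAP section 6.2, for analysis only and identically in both arms:

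- At any SOFA assessment made while the subject is on renal replacement therapy, set the renal item to 4 whatever the creatinine. With eligible baselines of 0 to 3, the renal change is then +4 to +1 and cannot read as improvement.
- Show the creatinine-only total as a sensitivity analysis.
- Tabulate new dialysis by arm beside the SOFA results.

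The cost is one scoring sentence, one derivation and one table. No subject's care changes.

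The condition is data. Before adopting the rule, confirm that dialysis status at Days 5, 15 and 29 is available for both arms from the hospital-interventions eCRF page or source records. The documents do not state this. The schedule has no dialysis row, the stopping rule in section 5.3.2 concerns Gamunex-C infusions only, and SAP section 7.5 names durations only for extracorporeal support and inotropes/vasopressors. Fluid output ("Daily 24-hour fluid balance (intake and output) while in hospital") is scheduled only through Day 10 and cannot stand in at Days 15 and 29. If dialysis were better captured in the IVIG arm, setting known cases to 4 would bias the comparison against IVIG.
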